1.3 Development of Levopront®

Levopront® is a drug of Dompe farmaceutici S.p.A., Italy, authorized in European Union, and established within the past two decades as a reliable and safe cough agent. The active ingredient (Levodropropizine) is a levorotary isomer of the dropropizine racemic mixture, and it is registered as a non-narcotic anti-cough agent of predominantly peripheral action. Levodropropizine suppresses coughing by inhibiting the stimulation of peripheral sensorial nerves and modulations of the neuropeptides involved in the coughing reflex. At the same time, it does not modify the spirometry parameters, the rheology of the bronchial secretion and the ciliary activity of the bronchial epithelium. Levodropropizine does not bind to beta-adrenergic,

muscarine, and opioid receptors, it does not have the affinity to H1-histamine and alpha-adrenergic receptors. The drug has less pronounced effect on the central nervous system, it has no effects on cardiovascular system and respiratory functional parameters, nor does it promote the development of drug dependence. The sedative effect of the drug is mild.

This Phase 3 clinical trial is designed to assess the non-inferiority of the efficacy and safety of Levopront® (Levodropizine) 30 mg/5 ml syrup in patients with non-productive cough associated with acute upper respiratory tract infection.

2 CLINICAL STUDY OBJECTIVES

2.1 Primary objective

To assess the efficacy of Levopront® in comparison with Libexin® based on daytime cough resolution rate by Day 8.

The daytime cough symptoms resolution corresponds to 0 or 1 points on the "Six-point daytime and nighttime cough assessment scale".

2.2 Secondary objectives

Secondary objectives of the study include treatment effect assessment in terms of the following efficacy and safety parameters:

- To assess the efficacy of Levopront® in comparison with Libexin® based on nighttime cough resolution rate by Day 8.
- Daytime and nighttime cough symptoms resolution according to "Six-point daytime and nighttime cough assessment scale" by Day 4.
- Change in severity and frequency of daytime and nighttime cough according to "Six-point daytime and nighttime cough assessment scale" on Day 4 and Day 8 from baseline on Day 1.
- Cough intensity change according to the visual-analogue scale on Day 4 and Day 8 from baseline on Day 1.
- Change of FEV1 on Day 8 from baseline values on Day 1.
- Rate of Adverse events (AE) and Serious Adverse Events (SAE) of the various severity according to subjective complaints, laboratory test results, physical examination, vital signs and spirometry.

3 STUDY DESIGN

3.1 Overall Study Design and Schedule

This is a multicenter open-label randomized comparative Phase 3 clinical trial in parallel groups. The study will be conducted at 8 Russian sites. The total expected number of enrolled patients is 184 (92 per each group). Taking into account the possibility of 20% screen-failure rate, up to 230 patients will be screened in the study.

3.1.1 Study Design

The study will consist of 3 periods: screening and randomization, study therapy, follow-up.

3.1.1.1 Screening and Randomization.

At Visit 1, Day 1 after signing the Informed Consent Form, the patients will be screened for assessment of inclusion/exclusion criteria. Demography, medical history, and information on concomitant medications will be collected; physical examination, vital signs, weight and height measurements will be performed; blood and urine samples for laboratory tests will be collected; the cough severity and frequency rate will be assessed using the "Six-point daytime and nighttime cough assessment scale"; cough intensity will be assessed using the visual-analogue scale; ECG and spirometry will be performed (pre- and post-bronchodilator) along with the chest x-ray or fluorography. Women of childbearing potential will take the pregnancy test before conducting the chest x-ray or fluorography.

According to the study schedule (considering acute condition of patients), screening and randomization will be performed in one day. Patients meeting all inclusion/exclusion criteria will be randomized into two groups (at a 1:1 ratio)

- Levopront® syrup 30 mg/5 ml — 10 ml t.i.d. for 7 days
- Libexin® 100 mg tablets — 1 tablet t.i.d. for 7 days

3.1.1.2 Study Treatment Period

The study drugs will be taken 3 times a day (with the interval of not less than 6 hours, between meals) during 7 days. The first study drug administration will be performed at the clinical site on the day of randomization; the last study drug administration will be performed in the evening before Day 8.

During the study treatment period, patients will keep a diary on a daily basis and fill in the cough severity and frequency data, body temperature, study drug dosing, concomitant medications and adverse events. Cough severity and frequency assessment should be performed in the morning after waking up using the "Six-point daytime and nighttime cough assessment scale" provided in the Diary and in the evening before retiring to bed. Patients will visit the clinical site on Days 4 and 8 for assessment of efficacy and safety parameters. Patients should bring the completed Diary and the unused study drug at each visit. During the visits, physical examination will be performed, vital signs will be assessed, cough severity and frequency assessment will be performed using the "Six-point daytime and nighttime cough assessment scale", and also cough intensity assessment will be made using the visual-analogue scale. On Day 8, blood and urine samples for laboratory tests will be collected, spirometry (without-bronchodilator) will be conducted, and then the study treatment period will be completed. If necessary, patients will continue treatment according to the local standards of medical care.

3.1.1.3 Follow-up Period

On Day 10, patients will be contacted by the Investigator via the telephone to follow-up for possible adverse events. After that, the patient's participation in the study will be over.

3.1.1.4 Study Diagram and Study Procedure Schedule

The summary of the study design and the study schedule are reported in Figure 1 and table 1, respectively

Figure 1. Study Diagram.

[figure not shown]

Table 1 Study Procedure Schedule, Protocol LDP0114

Visit (V)	Screening and randomization	Study treatment		Follow-up
	V1	V2	V3 ET or ED	TC
Day (D)	D1	D4	D8	D10
Visit window		± 1 day	± 1 day	± 1 day
Informed consent				
Patient's registration				
Demography data				
Medical history				
Physical examination				
Vital signs				
Body height and weight ⁵				
Cough severity and frequency assessment with the "Six-point daytime and nighttime cough assessment scale"				
Cough intensity assessment with the visual-analogue scale.				
Laboratory testing:				
- hematology				
- biochemistry				
- urinalysis				
- pregnancy test ¹				
ECG				
Spirometry ²				
Chest X-ray or fluorography ³				
Inclusion/exclusion criteria				
Randomization ⁴				
Study drug and Patient's dairy distribution to patient ⁴				
Return and accountability of the study drug, Patient's dairy review				
Concomitant medications assessment				
AE assessment				

Abbreviations: ET — end of treatment, ED — early discontinuation, ECG — electrocardiography, AE — adverse events, TC – telephone contact

Footnotes:

¹ Pregnancy test will be performed at the clinical site using the test-strip (only for the women of childbearing potential including the women in menopause of less than two years) before chest x-ray of fluorography.

² At visit Day 1 pre- and post-bronchodilator spirometry will be performed. At visit Day 8 only pre-bronchodilator spirometry will be performed.

³ Results of the chest x-ray or fluorography performed before signing the Informed Consent Form as a part of routine patient's examination for main disease (ARVI) can be used for the protocol purposes (if written conclusion report is available).

⁴ Patient's randomization and distribution of the study drug to the patient (along with the Patient's dairy) on Day 1 will be performed only after assessment of all inclusion/exclusion criteria. The first dose of the study drug will be taken at the clinical site.

⁵ The growth measure should be performed only during screening visit. For calculated values of lung function growth measured only at screening and weight measured during screening and Visit 3 (Day 8) should be used.

3.2 Justification of Study Design

This is an open-label randomized comparative clinical trial of the efficacy and safety of Levopront®, syrup 30 mg/5 mL and Libexin®, tablets 100 mg in patients with dry non-productive cough associated with acute respiratory infection of upper airways.

Patients from reference group will receive Libexin®. The choice of Libexin® is based on the similarity of its mechanism of action (it is a peripheral antitussive drug) and on the fact that it belongs to the same group in the International anatomical therapeutic chemical classification. Open design was chosen because of differences in the pharmaceutical forms of the investigational drugs and technical problems with blinding process of investigational products.

Study population includes patients with dry non-productive cough associated with non-complicated acute respiratory infection of upper airways. At Visit 1, Day 1 patients meeting inclusion/exclusion criteria will be enrolled into the study. During that period patients will receive either Levopront®, syrup 30 mg/5 mL or Libexin®, 100 mg tablets along with standardized concomitant treatment allowed by this protocol for 7 days, if necessary. Patients will keep a diary where they will record their condition using a "Six-point daytime and nighttime cough assessment scale". Assessment of the cough intensity with the visual-analogue scale will be done on each visit of the patients at the clinical site.

Patients with severe and chronic diseases of the respiratory system, burdened with smoking anamnesis, as well as patients who have indicated administration of the antibacterial therapy will not be included in the study.

Study drug dosing regimen and treatment duration of 7 days were chosen according to the European label. The treatment duration is necessary and sufficient to establish control over efficacy of antitussive therapy (frequency of resolution of cough symptoms) in acute respiratory infections of the upper respiratory tract. The intermediate evaluation of the efficacy will be held on Day 4.

The proportion of patients who responded to treatment, i.e. daytime cough symptoms resolution by Day 8 Visit was chosen as the primary efficacy endpoint. Resolution of daytime cough symptoms corresponds to score 0 or 1 at the Six-point daytime and nighttime cough assessment scale. The choice of primary and secondary study endpoints was based on WHO recommendations¹⁵, national guidelines "Pulmonology. National Guidelines", concise edition/ed. By A.G. Chuchalin. - M. : GEOTAR-Media, 201410, Guidelines for clinical trials ed. by A.N. Mironov⁷.

Besides the study will assess secondary efficacy endpoints according to spirometry, Diary and visual-analog scale. At the end of treatment, all patients will undergo a three-day follow-up period to assess the safety parameters.

The sample size is calculated for the primary efficacy endpoint - the proportion of patients with response to therapy (daily cough symptoms to visit Day 8), and the non-inferiority hypothesis to the efficacy^{19,22}.

The aim of this amended protocol is to provide justification of the increasing of the patients number in this study based on the results of the analysis, planned by the original protocol (Final version 1.0), that showed lack of power due to lower efficacy rate in both treatment groups than had been projected initially.

For this reason this analysis are considered interim analysis and an interim report will be issued to show these results. The full final report will be issued at the end of the study with the inclusion of the results of all patients.

The sample size estimation in the protocol amendment is based on the results of the study interim analysis that showed approximately 70% efficacy in both groups vs. 80% efficacy that had been projected initially. Thus the interim analysis at $\alpha = 0.05$ (one-sided) showed lack of power for the hypothesis testing ($< 80\%$).

In order to achieve power 80%, with corrected $\alpha = 0.025$ (one-sided), expected efficacy rate of 70% in both groups, non-inferiority margin $\delta = 20\%$, and ED rate not exceeding 10%, 184 patients should be enrolled in the study at 1:1 ration (92 patients per treatment group).

This approach complies with the general considerations for sample size re-estimation study designs (adaptive design used in both efficacy and BE studies). The alpha correction will provide the additional control over the type I error^{20,21}.

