## 2.2 SAMPLE SIZE

The sample size is calculated for the primary efficacy endpoint - the proportion of

 Citation from the protocol

patients with response to therapy (daily cough symptoms permission to visit Day 8) and non-inferiority hypothesis.

According to available data in the literature (Schroeder K., Fahey T. Over-the-counter medications for acute cough in children and adults in ambulatory settings) in clinical studies antitussives difference between the active treatment group and the placebo group was about 44%. In the placebo-controlled study (Smith SM, Schroeder K., Fahey T. Over-the-counter (OTC) medications for acute cough in children and adults in community settings) the difference between the active treatment groups and the placebo group was 25% and 35%. According to the meta-analysis of clinical trials of levodropropizine in two placebo-controlled studies the difference between the efficacy of the study drug and placebo was 45% in the pediatric population of patients (study Fiocchi) and 39% in the adult population of patients (study Allegra, where efficacy of levodropropizine was about 80%).

According to ICH guideline, the selected non-inferiority margin (non-inferiority margin) should not exceed the minimum difference between the performance indicators of the active drug and placebo. Based on the above data, non-inferiority margin  $\delta = 20\%$  was chosen for the study.

The sample size estimation in the protocol amendment is based on the results of the study interim analysis that showed approximately 70% efficacy in both groups vs. 80% efficacy that had been projected initially. Thus, the interim analysis at  $\alpha = 0.05$  (one-sided) showed lack of power for the hypothesis testing ( $< 80\%$ ).

The sample size was calculated using the formula for non-inferiority for comparison of two independent proportions:

$$n = \left( Z_{\frac{\alpha}{2}} + Z_{\beta} \right)^2 \times [p_1 \times (100\% - p_1) + p_2 \times (100\% - p_2)] / (p_1 - p_2 - \delta)^2$$

where  $n$  – sample size for each group,  $p_1$  – success rate in the control group,  $p_2$  – success rate in the treatment group,  $\delta$  – non-inferiority margin,  $Z_{\frac{\alpha}{2}}$  is 1.645 for one-sided  $\alpha = 0.05$  and  $Z_{\beta}$  is 0.84 for 80% power.

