### **3. INTERIM ANALYSIS, FINAL ANALYSIS AND UNBLINDING**

No interim analysis is planned.

There is open-label study. No unblinding required.

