### 7.2.3 Primary Efficacy Analysis

According to the Guideline EMA/EWP-482 (Superiority-non-inferiority and switching), in non-inferiority study primary analysis must be performed on Per-Protocol population (see chapter IV.1.4 Choice of analysis set of the guideline).

The main efficacy analysis population is defined as Per-Protocol (PP).

Study statistical testing hypothesis is expressed as:

H0: Lower bound of the 97.5% one-sided CI ( $p_1 - p_2$ )  $\leq -20\%$  => Non-inferiority rejected

H1: Lower bound of the 97.5% one-sided CI ( $p_1 - p_2$ )  $> -20\%$  => Non-inferiority accepted

The primary objective is to demonstrate the "non-inferiority" of Levopront® comparing to Libexin® with regards to the primary endpoint. For this purpose, the one-sided 97.5% Confidence Interval (CI) will be calculated for the two proportions difference — the rate of patients who responded to treatment (**cough absents**, when score is 0 or 1 at "six-point cough scale" vs. **cough presents**, when score is  $\geq 2$  at "six-point cough score") by Day 8 in the study treatment group and in the control group with a non-inferiority margin of  $\delta = 20\%$ . The null hypothesis (H0) that in the study treatment group the rate of treatment responders is less than in the control group, will be declined if the lower bound of the 97.5% one-sided CI for the two proportions difference is located to the right of the **-0.20**, with the final conclusion of non-inferiority of Levopront® versus Libexin®.

The proportion difference will be calculated using **Newcombes Hybrid Score** method (1998). See 8 [1].

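### Does the final one-sided 0.025 test still control type I error after the first-part analysis at one-sided 0.05?

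*Protocol*

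**What the plan says.** Protocol 3.3 dates the first part of the study (Part 1 below) from 09 November 2016 to 27 April 2017; the amended protocol is dated 14 September 2017. Protocol 3.2 explains that the analysis foreseen in version 1.0 was run on Part 1 at one-sided 0.05 and showed "lack of power due to lower efficacy rate in both treatment groups than had been projected initially". It continues: "For this reason this analysis are considered interim analysis and an interim report will be issued to show these results". The sample size was raised to 184, Part 1 patients stay in ("The full final report will be issued at the end of the study with the inclusion of the results of all patients"), and the final alpha becomes a corrected one-sided 0.025. Of that correction the protocol says: "The alpha correction will provide the additional control over the type I error", citing two references.

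The SAP repeats the basis for the new sample size in section 2.2, which "is based on the results of the study interim analysis that showed approximately 70% efficacy in both groups". Section 3 then says "No interim analysis is planned". The decision rule in SAP 7.2.3, as in Protocol 9.7.1, is that the null hypothesis "will be declined if the lower bound of the 97.5% one-sided CI for the two proportions difference" lies to the right of -0.20.

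**The concern.** Two analyses of accumating data, the first at 0.05 and the second at 0.025, do not by themselves give an overall error of 0.025. What they give depends on what the first could be used for. Here the first look was by arm, in an open-label trial, at its own alpha, and it was named interim only once its results were known. The documents give no Part 1 sample size, no Part 1 difference or bound, no overall alpha and no derivation of 0.025 from the two looks. A report of low power is not a test result. SAP section 3, read alone, seems to deny a look on which SAP 2.2 relies.

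At stake is the error rate attached to the primary conclusion. It will be reported as one-sided 0.025, and under some readings of the history it would be more than twice that.

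**Working it through.** **Inputs.** Response 70% in both arms, margin 20 points, Z values 1.96 and 0.84, early discontinuation 10% and 92 per arm come from Protocol 9.2. The Part 1 alpha of 0.05 and the earlier 80% response assumption come from Protocol 3.2 and 9.2. The Newcombe hybrid score bound comes from SAP 7.2.3. The Part 1 sample size is not in the documents and has to be assumed.

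**The plan's own figure.** n per arm = (1.96 + 0.84)² × (0.7 × 0.3 + 0.7 × 0.3) / 0.2² = 7.84 × 0.42 / 0.04 = 82.3. Dividing by 0.9 gives 91.5, so 92 per arm and 184 in total. SAP 2.2 prints 1.645 for alpha 0.05 beside the same formula; that value would give 2.485² × 0.42 / 0.04 = 64.8 per arm, so 184 rests on 0.025. The formula uses the 70% rate and an assumed difference of zero. The observed Part 1 difference does not enter.

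**Assumed size of Part 1.** The same formula at 80% response and alpha 0.05 gives (1.645 + 0.84)² × 0.32 / 0.04 = 49.4, so 50 per arm. At 70% response, 50 per arm has power Φ(0.2 / √(0.42/50) − 1.645) = Φ(0.54), about 70%, which agrees with the protocol's statement that power was under 80%. Against 83 evaluable per arm, the information fraction t is 50/83, about 0.6. Values from 0.3 to 0.9 show the range.

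**Overall one-sided error at the non-inferiority boundary.** The two test statistics are taken as bivariate normal with correlation √t, with critical values 1.645 at Part 1 and 1.960 at the end.

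| Reading | t = 0.3 | t = 0.6 | t = 0.9 |
|---|---|---|---|
| A. Only the final test can claim; extension follows the response rate | 2.5% | 2.5% | 2.5% |
| B. Extension only after Part 1 fails; only the final test can claim | 1.7% | 1.0% | 0.2% |
| C. Part 1 could have carried a claim at 0.05 | 6.7% | 6.0% | 5.2% |
| C, with the final test left at 0.05 | 8.6% | 7.7% | 6.3% |

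Reading D: no Part 1 claim, but the second-stage size is chosen freely from the observed difference, up to 184 in total. The worst case is 4.2%, 4.1% and 3.8% for a Part 1 total of 100, 112 and 130.

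**Check with the SAP's interval.** Simulated with the Newcombe bound at 83 or 92 per arm, at control and test rates of 70%/50% and 80%/60%, the final test alone has an error of 2.6% to 2.8%. For reading C at 70%/50% and 83 per arm, the either-look error is 7.2% with 25 per arm in Part 1, 6.9% with 50 and 5.6% with 75.

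**Which reading the documents support.** The only claim rule in the amended protocol and the SAP is the final 97.5% bound. The stated reason for extending is a lower response rate in both arms, and the formula turns that rate into exactly 184. This is reading A. Reading B also has only the final test able to claim, and shows that a decision to extend that was swayed by a failed look does no harm. With the final size fixed at 184, the probability of extending and then rejecting cannot exceed the probability that the final test rejects, which is 2.5%, whatever prompted the extension.

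**The case for a change.** The strongest reply is reading C. The Part 1 analysis was planned in version 1.0 with its own alpha, before anyone called it interim. Had it met the margin, a claim might have been made, and the procedure as a whole would then have an error of about 6%. The documents do not exclude this, and inference from the present claim rule is weaker than a statement. That much stands: whether Part 1 could have supported a claim is not recorded.

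It does not lead to a different plan. Under reading C the overall error cannot fall below the Part 1 alpha of 5%, whatever final alpha is chosen. At t = 0.6 the 0.025 final test adds only 6.0 − 5.0 = 1.0 point, against 7.7 − 5.0 = 2.7 points had it stayed at 0.05. The lower alpha therefore does give additional control, which is all the protocol sentence says.

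Reading D is harder to sustain, because 184 is what the formula yields from the response rate, with no room for a size picked from the difference.

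Nor is the role of Part 1 hidden. Protocol 3.2 says where the analysis came from, that it was used to re-estimate the sample size, that an interim report will show it, and that all patients enter the final report. It does not say whether that report will give the Part 1 sample size and bound. The two references cited for the correction cannot be checked here, so no weight is put on them. In SAP section 3, the statement on interim analyses reads naturally as no further look, since section 2.2 of the same document reports the completed one.

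**Conclusion.** The concern does not call for a change. An analyst following the plan runs one non-inferiority test, on the pooled data, at the one-sided 97.5% bound, with a nominal error of 2.5% and 2.6% to 2.8% by simulation with the specified interval. This rests on two things the documents indicate but do not spell out: that no claim depended on Part 1, and that the extension was sized from the response rate. If the first were false the error would be about 5% to 7%; if the second were false, up to about 4%. Both ranges depend on an assumed Part 1 size. The silence on what Part 1 could support, and the wording of SAP section 3, are gaps in the record. Filling them would alter no alpha, sample size, test or analysis set.
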